10.1.6.1 Quality Tolerance Limits

Quality Tolerance Limits will be defined in the Data Surveillance Plan.

10.1.7 Source Documents

Source documents provide evidence for the existence of the participant and substantiate the integrity of the data collected. Source documents are filed at the investigator's site.

Data reported in the eCRF that are transcribed from source documents must be consistent with the source documents or the discrepancies must be explained. The investigator may need to request previous medical records or transfer records, depending on the trial. Also, current medical records must be available.

The investigator must maintain accurate documentation (source data) that supports the information entered in the eCRF.

Trial monitors will perform ongoing source data verification to confirm that data entered into the eCRF by authorised site personnel are accurate, complete, and verifiable from source documents; that the safety and rights of participants are being protected; and that the trial is being conducted in accordance with the currently approved protocol and any other trial agreements, ICH GCP, and all applicable regulatory requirements.

10.1.8 Trial and Site Start and Closure

First Act of Recruitment

The trial start date is the date on which the clinical trial will be open for recruitment of participants.

The first act of recruitment is the first participant's first visit and will be the trial start date.

Trial/Site Termination

The sponsor or designee reserves the right to close the trial site or terminate the trial at any time for any reason at the sole discretion of the sponsor. Trial sites will be closed upon trial completion. A trial site is considered closed when all required documents and trial supplies have been collected and a trial site closure visit has been performed.

The investigator may initiate trial site closure at any time, provided there is reasonable cause and sufficient notice is given in advance of the intended termination.

Reasons for the early closure of a trial site by the sponsor or investigator may include but are not limited to:

For trial termination:

• Discontinuation of further IMP development.

For site termination:

- Failure of the investigator to comply with the protocol, the requirements of the IRB/IEC or local health authorities, the sponsor's procedures, or GCP guidelines.
- Inadequate or no recruitment (evaluated after a reasonable amount of time) of participants by the investigator.
- Total number of participants included earlier than expected.

If the trial is prematurely terminated or suspended, the sponsor shall promptly inform the investigators, the IECs/IRBs, the regulatory authorities, and any contract research organisation(s) used in the trial of the reason for termination or suspension, as specified by the applicable regulatory requirements. The investigator shall promptly inform the participant and should assure appropriate participant therapy and/or follow-up.

10.1.9 Publication Policy

A publication can be a journal manuscript, an abstract, a poster/presentation for a congress, or any openly accessible material.

A primary publication including the primary results of the trial (i.e. the results of the primary endpoint[s]) will be submitted for peer-reviewed publication within 12 months of DBL. The sponsor is responsible for this publication. All authors (trial responsible employees and/or applicable investigators and advisers) must fulfil the criteria for authorship from the International Committee of Medical Journal Editors (ICMJE).

The investigators may reach out to the sponsor to publish results that are not included in the primary publication. The investigator and the sponsor should agree on terms for data sharing and collaboration on such publications, as well as timing for release of the publication(s). In all cases, the sponsor retains the right to review and comment on the draft publication in due time before submission, but the investigator is not required to revise the draft accordingly, unless it discloses company confidential information or protected personal information, or may compromise intellectual property rights of the sponsor.

The sponsor may give researchers outside LEO Pharma access to anonymised data from this trial for further research according to the principles outlined by the European Federation of

Pharmaceutical Industries and Associations (EFPIA) (48). In that case, the researchers are obliged to attempt publication of the results obtained from their analyses.

The sponsor complies with Good Publication Practice (GPP3) standards and the recommendations from ICMJE.

10.1.10 Protocol Approval and Amendment

Before the start of the trial, the trial protocol and/or other relevant documents will be approved by the IEC/IRB/Competent Authorities, in accordance with local legal requirements. The sponsor must ensure that all ethical and legal requirements have been met before the first patient is enrolled in the trial.

This protocol is to be followed exactly. To alter the protocol, amendments must be written, receive approval from the appropriate personnel, and receive IRB/IEC/Competent Authority approval prior to implementation (if appropriate).

Administrative changes (not affecting the participant benefit/risk ratio) may be made without the need for a formal amendment. All amendments will be distributed to all protocol recipients, with appropriate instructions.

10.1.11 Liability and Insurance

The sponsor will take out reasonable third-party liability insurance cover in accordance with all legal requirements. The civil liability of the investigator, the persons instructed by him or her and the hospital, practice, or institute in which they are employed and the liability of the sponsor with respect to financial loss due to personal injury and other damage that may arise as a result of the carrying out of this trial are governed by the applicable law.

The sponsor will arrange for patients participating in this trial to be insured against financial loss due to personal injury caused by the pharmaceutical products being tested or by medical steps taken in the course of the trial.

10.1.11.1 Access to Source Data

During the trial, a monitor will make site visits to review protocol compliance, compare eCRF entries and individual participant's medical records, assess drug accountability, and ensure that the trial is being conducted according to pertinent regulatory requirements. eCRF entries will be verified with source documentation. The review of medical records will be performed in a manner to ensure that participant confidentiality is maintained.

Checking of the eCRF entries for completeness and clarity, and cross-checking with source documents, will be required to monitor the progress of the trial. Moreover, regulatory authorities of certain countries, IRBs, IECs, and/or the sponsor's Clinical Quality Assurance Group may wish to carry out such source data checks and/or on-site audit inspections. Direct access to source data will be required for these inspections and audits; they will be carried out giving due consideration to data protection and medical confidentiality. The investigator assures the sponsor, and Parexel if involved in monitoring/data management, of the necessary support at all times.

10.2 Appendix 2: Clinical Laboratory Tests

The tests detailed in Table 10-1 will be performed by a central laboratory.

Local laboratory results are only required in the event that the central laboratory results are not available in time for either IMP administration and/or response evaluation. If a local sample is required, it is important that the sample for central analysis is obtained at the same time. Additionally, if the local laboratory results are used to make either an IMP decision or response evaluation, the results must be recorded.

Protocol-specific requirements for inclusion or exclusion of participants are detailed in Section 5 of the protocol.

Additional tests may be performed at any time during the trial as determined necessary by the investigator or required by local regulations.

Investigators must document their review of each laboratory safety report.

Table 10-1 Protocol-required Safety Laboratory Tests

Laboratory Tests	Parameters	
Haematology	Thrombocytes	Leukocytes with differential count:
	Erythrocytes	Neutrophils
	Haemoglobin	Lymphocytes
	Haematocrit	Monocytes
	Erythrocyte indices:	Eosinophils
	Erythrocyte mean corpuscular volume (MCV)	Basophils
	Erythrocyte mean corpuscular haemoglobin (MCH)	
	% Reticulocytes	
Clinical chemistry	Urea nitrogen	AST/SGOT ²
	Potassium	Total and direct bilirubin ²
	Creatinine	ALT/SGPT ²
	Sodium	Prothrombin INR ²
	Glucose fasting ¹	Protein
	Calcium	Alkaline phosphatase ³
	Cholesterol (LDL, HDL total) fasting ¹	Gamma glutamyl transferase
	Triglycerides fasting ¹	Lactate dehydrogenase
		Albumin

Laboratory Tests	Parameters
Routine urinalysis	Specific gravity
	Glucose, protein, occult blood, ketones, nitrite, leukocytes by dipstick
	Urine samples will be tested at the trial site (dipstick). It will be at the investigator's discretion to decide whether a urine sample should be sent to the central laboratory for microscopic examination (WBC; RBC; epithelial cells, squamous; epithelial cells, transitional; epithelial cells, renal tubular; hyaline casts; WBC casts; RBC casts; waxy casts; granular casts; calcium oxalate crystals; uric acid crystals; triphosphate crystals; yeast; and bacteria).
Pregnancy testing (WOCBP only)	Highly sensitive urine hCG pregnancy test (as needed for women of childbearing potential) at timepoints detailed in Section 8.3.5. ⁴
Other screening tests	Follicle-stimulating hormone and oestradiol (as needed in women of non-childbearing potential only)
	Serology (HIV-1 antibody, HIV-2 antibody, HBsAg, HCV antibody)
	Immunoglobulin E
	Thyroid-stimulating hormone, thyroxine
	Retinol

- 1. Participants should be fasting for at least 8 hours prior to the collection of samples for analysis of fasting values of triglycerides, cholesterol, and glucose. Participants will be reminded of fasting requirement the day before the visit. If they do not follow fasting requirements on the visit day, they will be asked to return to the site in fasting conditions (within the visit time window), so fasting blood samples can be collected.
- 2. Details of liver chemistry stopping criteria and required actions and follow-up are given in Section 7.1 and Appendix 6. All events of concurrent measurements of ALT and/or AST ≥3×ULN with total bilirubin ≥2×ULN or prothrombin INR >1.5, which may indicate severe liver injury (possible Hy's Law), should be reported as an SAE without undue delay and no later than within 24 hours (see Section 10.3.4 for reporting of SAEs).
- 3. If alkaline phosphatase is elevated, consider fractionating.
- 4. Local urine testing will be standard for the protocol unless serum testing is required by local regulation or IRB/IEC. The test should have a minimum sensitivity of 25 mIU/mL.

Abbreviations: ALT= alanine aminotransferase; AST=aspartate aminotransferase; BUN=blood urea nitrogen; HBsAg=hepatitis B virus surface antigen hCG=human chorionic gonadotropin; HCV=hepatitis C virus; HDL=high-density lipoprotein; IEC=independent ethics committee; INR=international normalised ratio; IRB=institutional review board; LDL=low-density lipoprotein; RBC=red blood cell; SGOT=serum glutamic-oxaloacetic transaminase; SGPT=serum glutamic-pyruvic transaminase; WBC=white blood cell; WOCBP=woman of childbearing potential.

10.3 Appendix 3: AEs and SAEs: Definitions and Procedures for Recording, Evaluating, Follow-up, and Reporting

10.3.1 Definition of AE

An AE is defined as any untoward medical occurrence in a patient or clinical investigation participant administered a pharmaceutical product and which does not necessarily have a causal relationship with this treatment. An AE can therefore be any unfavourable and unintended sign (including an abnormal laboratory finding), symptom, or disease temporally associated with the use of a medicinal (investigational) product, whether or not related to the medicinal (investigational) product (ICH E2A guidelines).

This definition includes:

- Accidental injuries.
- Events related to trial procedures.
- Reasons for any unfavourable and unplanned change in medication (drug and/or dose).
- Clinically significant worsening of pre-existing conditions.
- Reasons for admission to hospital or surgical procedures unless these were planned before the participant consented to trial participation.
- AEs commonly observed and AEs anticipated based on the pharmacological effect of the IMP.
- Any laboratory abnormality assessed as clinically significant by the investigator (see Section 8.2.4).

10.3.2 Definition of SAE

An SAE is any untoward medical occurrence that:

- Results in death.
- Is life-threatening at risk of death at the time of the SAE (not an event that hypothetically might have caused death if more severe).

• Requires in-patient hospitalisation or prolongation of existing hospitalisation.

Notes:

- Hospitalisation for procedures or treatments planned prior to the participant consented to trial participation does not constitute an AE and should therefore not be reported as an AE or SAE.
- Hospitalisation for elective treatment of a pre-existing condition which did not worsen from the participant consented to trial participation is not considered an AE and should therefore not be reported as an AE or SAE, even if not planned before consent to trial participation.
- Hospitalisation for routine scheduled treatment or monitoring not associated with any aggravation of the condition does not constitute an AE and should therefore not be reported as an AE or SAE.
- Hospitalisation for administrative purpose does not constitute an AE and should therefore not be reported as an AE or SAE.
- Complications that occur during hospitalisation are AEs. If a complication prolongs hospitalisation, the event is an SAE.
- When in doubt as to whether hospitalisation occurred, the AE should be considered serious.
- Results in persistent or significant disability or incapacity.
- Is a congenital anomaly or birth defect.
- Is a medically important condition. Events that may not be immediately life-threatening or result in death or hospitalisation but may jeopardise the participant or may require intervention to prevent one of the other outcomes listed in the definition above. Examples are intensive treatment in an emergency room or at home for allergic bronchospasm, blood dyscrasias, and convulsions that do not result in hospitalisation, development of drug dependency, or drug abuse.

Additionally, all malignancies, including skin malignancies, should be reported as SAEs.

10.3.3 Recording and Follow-up of AE and SAE

AE and SAE Recording

AEs must be assessed by a physician.

When an AE/SAE occurs, it is the responsibility of the investigator to review all documentation (e.g. hospital progress notes, laboratory, and diagnostics reports) related to the event.

AEs reported by the participant or observed by the investigator must be recorded on the AE form of the eCRF and should be described in the following manner:

The AE term must be in precise English medical terminology (that is, not necessarily the exact words used by the participant). Whenever possible, a specific diagnosis should be stated (e.g. 'allergic contact dermatitis').

For cutaneous AEs, the location must be part of the AE description and may be described as (e.g. the face, scalp, back, chest, arm, leg, trunk, or limb). Additionally, for participants treated with delgocitinib cream, the location should be described using the following terminology:

- Lesional/perilesional (\le 2 cm from the border of lesion(s) treated with IMP).
- Distant (>2 cm from the border of lesion(s) treated with IMP).

The duration of the AE must be reported by the start date and stop date of the event, unless the event is ongoing. If the event is ongoing, it will be marked as ongoing. In addition, it will be recorded if the AE started prior to first administration of IMP.

AEs must be classified in terms of severity, causality, and outcome according to the definitions provided below.

Action taken with IMP: any action taken with IMP as a consequence of the AE must be recorded (dose not changed, drug withdrawn, not applicable, unknown).

Withdrawal from trial due to this AE: it must be recorded whether the AE led to withdrawal from the trial.

Other action taken: any other action taken as a result of the AE must be recorded (none, concomitant medication, concurrent procedure).

Assessment of Severity

The severity of the AE should be described in terms of mild, moderate, or severe according to the investigator's clinical judgement. If the AE worsens in severity, the new severity including

date of worsening, should be recorded. However, if an AE with onset prior to IMP initiation worsens after IMP administration, a new AE should be recorded:

Mild: An AE that is usually transient and may require only minimal treatment or therapeutic intervention. The event does not generally interfere with usual activities of daily living.

Moderate: An AE that is usually alleviated with additional specific therapeutic intervention. The event interferes with usual activities of daily living, causing discomfort, but poses no significant or permanent risk of harm to the participant.

Severe: An AE that interrupts usual activities of daily living, or significantly affects clinical status, or may require intensive therapeutic intervention. An event is defined as 'serious' when it meets at least 1 of the predefined outcomes as described in the definition of an SAE, NOT when it is rated as severe.

Assessment of Causality

The investigator is obligated to assess the relationship between trial treatment and each occurrence of each AE/SAE. The investigator will use clinical judgement to determine the relationship.

A *reasonable possibility* of a relationship conveys that there are facts, evidence, and/or arguments to suggest a causal relationship, rather than a relationship cannot be ruled out.

Alternative causes, such as underlying disease(s), concomitant therapy, and other risk factors, as well as the temporal relationship of the event to trial treatment administration will be considered and investigated.

The investigator will also consult the delgocitinib IB or the SmPC for alitretinoin (Toctino[®]) in their assessment.

For each AE/SAE, the investigator must document in the medical notes that he/she has reviewed the AE/SAE and has provided an assessment of causality.

There may be situations in which an SAE has occurred, and the investigator has minimal information to include in the initial report in the EDC tool. However, it is very important

that the investigator always make an assessment of causality for every event before the initial recording of the SAE data in the EDC tool.

The investigator may change their opinion of causality in light of follow-up information and send an SAE follow-up report with the updated causality assessment.

The following decision choices will be used by the investigator to describe the causality assessment:

Probably related:

- Follows a reasonable temporal sequence from administration of the IMP.
- Could not be reasonably explained by the participant's clinical state, environmental or toxic factors, or other therapies administered to the participant.
- Follows a known pattern of response to the IMP.
- Disappears or decreases on cessation or reduction in dose of the IMP.
- Reappears or worsens upon re-challenge.

Possibly related:

- Follows a reasonable temporal sequence from the administration of the IMP.
- Could also be reasonably explained by the participant's clinical state, environmental or toxic factors, or other therapies administered to the participant.
- Follows a known pattern of response to the IMP.

Not related:

- Does not follow a reasonable temporal sequence from administration of the IMP.
- Is better explained by other factors like the participant's clinical state, environmental or toxic factors, or other therapies administered to the participant.
- Does not reappear or worsen upon re-challenge.
- Does not follow a known pattern of response to the IMP.

The causality assessment is one of the criteria used when determining regulatory reporting requirements.

Assessment of Outcome

The outcome of the event according to the investigator's clinical judgement should be classified using the categories below.

Recovered/resolved: The event has stopped. The stop date of the event must be recorded.

Recovering/resolving: The participant is clearly recovering from an event. The event is not yet completely resolved.

Not recovered/ not resolved: Event is still ongoing.

Recovered/ resolved with sequelae: The event has reached a state where no further changes are expected and the residual symptoms are assumed to persist. An example is hemiparesis after stroke.

The stop date of the event must be recorded. In case of an SAE, the sequelae should be specified.

Fatal: The participant has died as a consequence of the event. Date of death is recorded as stop date for the AE.

Unknown: Unknown to investigator, e.g. participant lost to follow-up.

The sponsor's definitions versus Clinical Data Interchange Standards Consortium (CDISC) definitions: Note that as per the above definition, the sponsor uses 'recovered/resolved' only if an event has actually stopped. According to the CDISC definition, the category 'recovered/resolved' also includes events which have improved. However, following the sponsor's definitions above, such an improved event will instead be classified as 'not recovered/not resolved' or 'recovering/resolving'.

Similarly, it should be noted that as per the above definition, the sponsor uses 'recovered/resolved with sequelae' only if an event has reached a state where the residual symptoms are assumed to persist. According to CDISC, an event is considered 'with sequelae', if it has 'retained pathological conditions'. Consequently, it is likely that some of the events classified by the sponsor with the outcome 'recovered/resolved with sequelae' could have been classified with the outcome 'recovered/resolved' according to the CDISC definition.

In summary, the definitions used by the sponsor are more conservative than those used by CDISC.

Follow-up of AE and SAE

The investigator is obligated to perform or arrange for the conduct of supplemental measurements and/or evaluations as medically indicated or as requested by the sponsor to elucidate the nature and/or causality of the AE or SAE as fully as possible. This may include

additional laboratory tests or investigations, histopathological examinations, or consultation with other health care professionals.

If a participant dies during participation in the trial or during a recognised follow-up period, the investigator will provide the sponsor with a copy of any post-mortem findings including histopathology.

New or updated information will be recorded in the originally completed form.

The investigator will submit any updated SAE data to the sponsor within 24 hours of receipt of the information.

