2.3.3 Overall Benefit/Risk Conclusion

Taking into account the measures taken to minimise risk for the trial participants, the potential risks identified in association with delgocitinib and alitretinoin are justified by the anticipated benefits that may be afforded to participants with severe CHE, and more generally the potential benefits to patients with moderate to severe CHE in the future.

3 Objectives and Endpoints

Table 3-1 Primary Objective and Estimands for Primary Endpoint and Key Secondary Endpoints

Objectives	Estimand type and strategy	Endpoints
Primary objective: To compare the efficacy and health-related quality of life of twice-daily topical application of delgocitinib cream with once-daily oral administration of alitretinoin capsules in the treatment of patients with severe CHE.	Primary. 'Composite' strategy. First supplementary. 'Pandemic modified composite' strategy. Second supplementary (for endpoints at Week 12 and Week 24). 'Treatment policy' strategy.	Primary endpoint: Change in HECSI score from baseline to Week 12. Key secondary endpoints: HECSI-90 at Week 12. IGA-CHE TS at Week 12. Change in HESD itch score (weekly average) from baseline to Week 12. Change in HESD pain score (weekly average) from baseline to Week 12. AUC of HECSI-90 from baseline up to Week 24. AUC of change from baseline in DLQI score up to Week 24. Change in HECSI score from baseline to Week 24.

Abbreviations: AUC=area under the curve; CHE=chronic hand eczema; DLQI=Dermatology Life Quality Index; HECSI=Hand Eczema Severity Index; HECSI-90=at least 90% improvement in HECSI score from baseline; HESD=Hand Eczema Symptom Diary©; IGA-CHE=Investigator's Global Assessment for chronic hand eczema©; IGA-CHE TS=IGA-CHE treatment success.

Table 3-2 Secondary and Exploratory Objectives and Endpoints

Objectives	Endpoints				
Secondary objective: To compare the safety of twice-daily topical application of delgocitinib cream with once-daily oral administration of alitretinoin capsules in the treatment of patients with severe CHE.	 Secondary endpoints: Number of treatment-emergent AEs from baseline up to Week 26. Number of treatment-emergent SAEs from baseline up to Week 26. Number of AEs leading to IMP discontinuation up to Week 24. 				
Exploratory objectives:	Exploratory endpoints:				

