6.2 Preparation, Handling, Storage, and Accountability

6.2.1 Administration of Trial Treatment

6.2.1.1 Delgocitinib Cream

Delgocitinib cream 20 mg/g will be applied as a twice-daily topical application for up to 24 weeks. The applications will be performed approximately 12 hours apart. Instructions for use will be provided.

Delgocitinib will be applied to clean, dry hands, fingers, fingertips, and wrists in a thin layer covering the affected area(s). The amount of delgocitinib to be used depends on the size of the affected area(s) and the size of the hands, fingers, fingertips, and wrists. 1 tube of 30 g delgocitinib cream is considered sufficient for treatment of the whole surface of hands,

^{1. 10} mg will only be used in participants with unacceptable adverse reactions after the dose of 30 mg (see Section 6.5).

fingers, fingertips, and wrists twice-daily for 2 weeks; however, a few participants may need more (based on experience from the LP0133-1273 trial), which will be allowed at the discretion of the unblinded investigator.

The first application of delgocitinib will occur at the trial site under supervision of the unblinded investigator or delegate. Prior to the first application of delgocitinib cream, the participant will be instructed how much cream to apply and which area(s) to treat.

Prior to the first application of IMP at baseline, the investigator will determine the treatment area(s) on the left and the right hand using the following 5 areas: fingertips, fingers (except fingertips), palm of hands, back of hands, and wrists. The treatment areas affected will be marked on a scheme showing the back and the front of the left and the right hand as from the perspective of the participant. If new CHE lesions occur, the scheme will be updated to document these.

Only the affected area(s) on the hands, fingers, fingertips, and wrists will be treated. If new lesions occur on initially untreated area(s) of the hands, fingers, fingertips, and wrists, these new lesions will be treated with delgocitinib as well. The participants will be advised to contact the unblinded investigator before initiating treatment of new lesions.

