6.5 Dose Modification

Delgocitinib: Dose modifications are not possible with the delgocitinib cream, but the amount of cream applied to the hands may be increased, if new lesions appear, at the discretion of the unblinded investigator (see Section 6.2.1.1).

Alitretinoin: The dose of alitretinoin may be reduced from 30 mg to 10 mg in participants with unacceptable adverse reactions. If the dose is decreased, it will not be permitted to increase the dose at a later point during the trial. Alitretinoin dose reductions and the reason for dose reduction will be reported in the eCRF.

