If 'adverse event' is selected, the AE in question will be linked to the discontinuation of IMP. If 'other' is selected as a reason, a specification must be provided in the eCRF.

It will also be recorded whether the discontinuation of IMP was related to the COVID-19 pandemic to support the statistical analysis.

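### The AE action-taken list in 10.3.3 cannot record an alitretinoin dose reduction that 6.5 allows; secondarily, 9.3.5 leaves open whether planned treatment gaps count as exposure

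*Combined protocol and SAP*

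**What the plan says.** On recording: for each AE, 10.3.3 requires that "any action taken with IMP as a consequence of the AE must be recorded (dose not changed, drug withdrawn, not applicable, unknown". Section 6.5 states that "The dose of alitretinoin may be reduced from 30 mg to 10 mg in participants with unacceptable adverse reactions", and the Table 6-1 footnote says that 10 "mg will only be used in participants with unacceptable adverse reactions after the dose of 30 mg". Section 10.3.1 includes among AEs "Reasons for any unfavourable and unplanned change in medication (drug and/or dose". The reduction itself is captured: "Alitretinoin dose reductions and the reason for dose reduction will be reported in the eCRF". For the other arm, 6.5 says "Dose modifications are not possible with the delgocitinib cream".

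For permanent discontinuation with an AE as the reason, 7.1 adds that "the AE in question will be linked to the discontinuation of IMP". No similar sentence covers dose reductions.

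On reporting: Table 3-2 has as a secondary safety endpoint "Number of AEs leading to IMP discontinuation up to Week 24". Section 9.3.11.1 plans tables of all AEs, SAEs, related AEs, AESIs, and AEs leading to trial withdrawal or permanent discontinuation. The one listing said to show action taken with the IMP covers the last two groups.

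On exposure: 9.3.5 counts days from the first to the last administration within a given week interval, both ends included, and presents days of exposure by treatment group. It does not say which intervals are used for that count, or how a total is formed. Sections 6.2.1.1, 6.2.1.2 and 6.5.1 recommend stopping at IGA-CHE 0 or 1 (after 16 weeks of delgocitinib, 12 of alitretinoin) and require a restart on relapse.

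**The concern.** Comparing safety between the arms is the secondary objective. Alitretinoin has two responses to a poorly tolerated dose, reduction and discontinuation; delgocitinib has no dose reduction. An AE managed by reduction falls outside the discontinuation endpoint, by that endpoint's definition. It should then be visible somewhere as an AE that changed treatment. As planned, its action field is wrong or uninformative, and no described table picks it out. The loss falls on one arm.

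The exposure table is read beside the AE counts. If off-drug days inside a planned stop and restart are counted as exposure, restarters appear to have been treated for longer than they were. The amount depends on an interval choice that the plan leaves open.

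**Working it through.** The plan states no figure on either point, so there is none to reproduce.

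**AE action field.**

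1. Under 6.5 and the Table 6-1 footnote, the 10 mg dose is used only after unacceptable adverse reactions to 30 mg.
2. Under 10.3.1, the reason for an unfavourable, unplanned dose change is an AE. Each reduction therefore has a triggering AE.
3. For that AE, 'dose not changed' and 'drug withdrawn' are false, 'not applicable' is wrong because an action was taken, and 'unknown' is wrong because the site knows it.
4. The same section lists improvement after a lower dose among the features of a probably related event, so it foresees an action that its own list cannot hold.

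Scale: 9.5 gives 255 participants per arm. The reduction rate is an assumption: 255 × 0.05 = 12.75 (13) and 255 × 0.15 = 38.25 (38).

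**Exposure.** The 9.3.5 rule, summed over intervals that contain a dose, is: days = Σ (last dosing day − first dosing day + 1). Visit days come from the SoA (1, 8, 15, 29, 57, 85, 113, 141, 169). The dosing calendars are assumed, with the last dose on Day 168.

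| Last dose before gap, restart | On drug | One 24-week interval | Intervals cut at SoA visit days |
|---|---|---|---|
| Day 84, Day 113 (alitretinoin) | 84 + 56 = 140 | 168 (168/140 − 1 = 20%) | 140 |
| Day 112, Day 141 (either arm) | 112 + 28 = 140 | 168 (20%) | 140 |
| Day 84, Day 141 (alitretinoin) | 84 + 28 = 112 | 168 (168/112 − 1 = 50%) | 112 |
| Day 113, Day 127 (delgocitinib) | 113 + 42 = 155 | 168 (168/155 − 1 = 8.4%) | 168 (8.4%) |
| Day 88, Day 110 (alitretinoin) | 88 + 59 = 147 | 168 (168/147 − 1 = 14%) | 168 (14%) |

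- Row 2 also depends on coarser cuts: a Weeks 0-12/12-24 split counts 168, and a Weeks 0-16/16-24 split counts 140.
- Row 4 follows from 6.2.1.1, which has the cream applied at home before each visit. A participant who stops at the Day 113 visit has normally dosed that day. With an unscheduled restart on Day 127, doses lie on both sides of the gap within Days 113-140. If the restart is instead at the Day 141 visit, the interval holds one dosing day and nothing is overcounted.
- Row 5 uses the ±3-day visit window with cuts at nominal days. Days 85-112 count as 28, against 4 + 3 = 7 on drug.

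A gap is thus counted only when doses fall on both sides of it within the same interval.

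Arm level, with one 24-week interval, if 10-30% restart after a 28-day gap and all others take 168 days (assumed): the true means are 168 − 28 × 0.10 = 165.2 and 168 − 28 × 0.30 = 159.6. The overstatement is 2.8 to 8.4 days (168/165.2 − 1 = 1.7%; 168/159.6 − 1 = 5.3%).

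**The case against.** The strongest reply on recording is that nothing is lost: 6.5 puts the reduction and its reason in the eCRF, the AE carries its own dates, and it remains in the all-AE tables and participant listings. That stands, and a reader who inferred that reductions go unrecorded would be wrong. What remains is a required field with no true answer, and two records that must be matched without a stated key.

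Section 9 also calls itself a summary and defers detail to an SAP whose text is not in the reviewed document. A later SAP could add a table of AEs leading to reduction or define the intervals. It could not add an option to a list that the protocol fixes at data collection. It is also fair that a dose-reduction table would have entries in one arm only and that the discontinuation endpoint leaves reductions out by design. The table would be descriptive.

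On exposure, a reader might infer that 9.3.5 never removes a planned gap. The text does not support this: the rule works within an interval, and with visit-day cuts the first three gaps above drop out completely. The opposite inference, that visit-aligned intervals always remove the gap, fails in rows 4 and 5. Restarters are also not hidden, since 9.3.3 reports their number by arm.

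**Conclusion.** The inconsistency between 10.3.3 and 6.5 is real and needs no assumption. Followed as written, the plan miscodes the action taken for each AE that leads to an alitretinoin reduction, states no AE link of the kind 7.1 has for discontinuation, and describes no tabulation that identifies these AEs. Its frequency is unknown; 13-38 participants holds only under the assumed 5-15%.

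The exposure point is secondary and conditional. The defect is that off-drug days between doses in the same interval are not subtracted while the intervals and the total are undefined. For restarters, the error in the cases worked ranges from none to 20% or 50%, and the last two figures require a single 24-week interval. Non-restarters are unaffected.

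A reader might carry this over to efficacy or to AE incidence rates. The documents do not support that: 9.3.11.1 bases event rates on observation time, and no efficacy test, type I error or power calculation uses these fields. The effect is confined to descriptive safety summaries, and the changes should be made on that basis.

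**What to change.** - **10.3.3:** reconcile with 6.5 by adding 'dose reduced' to the action-taken list, or by linking the dose-reduction record to the triggering AE as 7.1 does for discontinuation.
- **9.3.11.1:** summarise or list AEs leading to dose reduction.
- **9.3.5:** define the intervals and how a total is formed. Report on-treatment days with planned stop-restart gaps removed, beside first-to-last duration. The daily eDiary treatment days (6.4) supply the dates; an isolated missed entry should not be read as a gap.

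These changes affect recording and reporting only, not any dose or stopping rule. The cost is one form change or record link, one extra AE summary and modest programming. If the trial is running, reductions already made need some retrospective entry. The report will also carry two exposure figures that need explaining.
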